6.2 Analysis methods

Main analysis of treatment effects will be performed on an intention to treat basis. Crude change in outcomes for both groups from baseline to post-treatment and follow up will be provided as mean change scores with standard deviations or proportions.

Main analysis of primary outcome

The primary outcome will be analyzed with constrained longitudinal data analysis (cLDA), i.e. a linear mixed effects model with a random intercept for subject will be fitted to regress 6MWD at baseline and 6 weeks on study center, time point of assessment and an interaction of time point and intervention group.(7, 19) A mere group effect as in regular LDA such as repeated measures ANOVA is not included thus constraining baseline means for groups to be equal. This type of

model adjusts for baseline mean differences in the outcome between intervention groups similar to analysis of covariance (ANCOVA). In fact, it is equivalent to ANCOVA in the absence of missing outcome data. In the presence of missing data cLDA in contrast to ANCOVA considers all available data in the estimation of the common baseline mean and avoids listwise deletion of cases lost to follow up.

Main analysis of secondary outcomes

For analysis of the overall trajectory of 6MWD until final follow at 24 weeks, data from all time points will be considered and terms for the 24 week time point and its interaction with intervention group will be added to the above model. Secondary continuous outcomes (pulmonary function parameters, lower limb muscle strength as time in seconds remaining in squatting position, and SF-12 composite scores) will be analyzed analogously, estimating treatment effects at 6 weeks and 24 weeks simultaneously. Occurrence of a favorable outcome with regard to dyspnea (mMRC) will be analyzed with longitudinal logistic regression(20). Estimates of treatment effects and changes in mean scores (continuous outcomes) or percentages (discrete outcomes) from baseline to 6 weeks and 24 weeks follow up by intervention group will be provided with 95% confidence intervals. Residuals of all linear models will be checked for normal distribution using qq-plots; if this assumption is violated robust standard errors (Huber-White sandwich estimator) will be calculated.

Adjustments

All main analysis of treatment effects will be adjusted for study center (as fixed effect).

Corrections for multiplicity

No corrections for multiple testing will be applied.

Missing data

As mixed effects models are used for analysis of treatment effects and listwise deletion of cases with missing data is thus avoided, main analysis will be performed on available (unimputed) data, assuming that data are missing at random (MAR) and missing values depend on observed variables in the model (center, time point, and the interaction of group and time point)(21, 22). This assumption will be tested in sensitivity analysis (see below).

Sensitivity analysis and per protocol analysis

Two types of sensitivity analysis will be performed. First, above analyses will be repeated on 50 multiply imputed datasets(23) whereas imputation is based on available outcome data as well as available baseline information including variables not included in the analysis models. This compares the simple MAR assumption outlined above with an extended MAR assumption, i.e. that missing values are also dependent on observed (auxiliary) variables not included in the models used for primary analysis. Apart from center, these auxiliary variables comprise gender, age, disease severity, time from first hospital admission for Covid-19 to baseline assessment, presence of comorbidities, smoking history, and body mass index. Imputation is preferred over adjustment within the mixed models (adding covariates) as conditioning on covariates is not intended given this is a pragmatic trial and to avoid overfitting of the models. Chained equations will be used for simultaneous imputation of all missing outcome data. Second, reference-based multiple imputation will be used for simulating a non-missing at random (NMAR) scenario where patients with missing assessments in the intervention group are supposed to experience change in the outcome that is similar to that observed in the control group after the last available data point before dropout. This is called copy increments in reference (CIR) approach. Imputation is based on a joint multivariate normal distribution of the outcome for each treatment arm. In the case of CIR those in the intervention group are supposed to switch to the distribution of the control group after dropout(24). CIR imputation is done separately for each outcome and considering center and auxiliary covariates specified for extended MAR imputation. Per protocol analysis will also be performed estimating the previously specified models on data including only those participants from the intervention group who had adhered to the TEREKO protocol as defined above.

Sub-group analysis

Due to lack of power for this type of analysis, no pre-specified sub-group analysis will be performed.

Analysis of harms

Patients in the intervention group can actively report adverse events to the responsible doctor at any time through the smart phone app or contact the responsible doctor, clinical department, or

researcher by phone or WeChat. Patients in the control group can actively report adverse events by contacting the responsible doctor, the clinical department, or the researcher by phone or WeChat. In addition, all patients will be asked at 2 and 4 weeks telephone consultations, at the 6 weeks post-treatment assessment and at 24 weeks follow-up assessment if any adverse events occurred during the previous period. Severity and relationship with intervention of these adverse events will be evaluated by two independent doctors otherwise uninvolved in the trial. Conflicts will be resolved by consensus or if not possible by consultation of a third reviewer.

Proportions of patients reporting any adverse events and serious adverse events during the whole study period, during the intervention period, and during the follow up period stratified by intervention group as randomized will be reported. Number of adverse events per patient reporting any such events will also be given as well as types/severity of events and supposed relationship with interventions.

Software

All analyses will be performed with Stata 14 (Stata Corporation, Texas, USA).

VII. REFERENCES

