3.1 Design

Pragmatic, multi-center, randomized-controlled, 1:1 parallel group trial. The control group receives educational instructions for daily living at baseline. The intervention group participates in a 6-weeks, home-based, remotely monitored exercise program for cardiopulmonary rehabilitation, delivered via smartphone (R+ health app software) with 3-4 sessions per week and monitored remotely in real-time via a heart rate device worn on the body of the patient. Exercises types include breathing control and thoracic expansion, aerobic exercise, and muscle strength exercises. Exercise difficulty, intensity, and duration is scheduled to increase over time.

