3.3 Sample size calculation

Sample size is calculated for the primary outcome 6 minute walking distance (6MWD) measured with 6 minutes walking test (6MWT). A systematic review on measurement properties of field walking tests conducted by the European Respiratory Society and American Thoracic Society(6) found a median minimal important difference (MID) of 30 meters for the 6MWT (range 22-57 meters) across studies using anchor- or distribution-based approaches in different lung disease including COPD, pulmonary arterial hypertension, and interstitial lung disease. Since an MID for 6MWT in COVID-19 has not been established at the time of the development of the TEREKO protocol and learning effects may also occur (particularly in the exercise group), a larger and thus more conservative MID of 50 meters is supposed here. A standard deviation of change in 6MWD over six weeks of 99 meters in controls and 71 in the intervention group as reported in a previous trial on the effectiveness of an exercise program in SARS survivors(3) is further assumed. The assumption of a greater standard deviation in controls makes sense in so far as a greater variety of outcomes can be expected in this group due to greater variations in disease course and environmental influences as these are not influenced by a targeted intervention. With a power of 80% and an alpha error of 5% this yields a sample size of 96 participants respectively 48 per group to detect a statistically significant signal for a difference in change in 6MWD between

groups with an independent samples t-test. This corresponds to power analysis for ANCOVA or constrained longitudinal data analysis for high correlations ($r \geq 0.8$) between repeated measurements(7, 8). An assumption of such high correlation is conservative and justified given that we have no previous knowledge about the effectiveness of similar interventions in the target population. Assuming an attrition rate of 20% the recruitment target is 120 participants or about 60 per group.

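### The random-intercept cLDA for the primary outcome matches ANCOVA only if the 6MWD variance is the same at baseline and week 6; otherwise the primary CI and p-value may be mis-sized in either direction

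*SAP*

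**What the plan says.** SAP section 6.2 (main analysis of the primary outcome) specifies "a linear mixed effects model with a random intercept for subject will be fitted to regress 6MWD at baseline and 6 weeks", with fixed effects for centre, time point and the time-by-group interaction and no group main effect. It names no residual covariance structure. Of this model it says: "In fact, it is equivalent to ANCOVA in the absence of missing outcome data". The same section extends the model to 24 weeks and applies it to every continuous secondary outcome. Huber-White standard errors are to be used only if qq-plots show non-normal residuals.

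Section 3.3 plans with "A standard deviation of change in 6MWD over six weeks of 99 meters in controls and 71 in the intervention group" and argues that the larger spread in controls is to be expected. It relates the t-test calculation to the planned model: "This corresponds to power analysis for ANCOVA or constrained longitudinal data analysis for high correlations", with r of at least 0.8. Section 3.1 sets 1:1 allocation. The SAP gives no SD of 6MWD at baseline or at week 6.

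**The concern.** A random intercept plus a single residual variance is a compound-symmetry model: one total variance for both visits and both arms. The claimed equivalence to ANCOVA belongs to cLDA with an unstructured covariance over visits. There the joint likelihood splits into a baseline part and a part for week 6 given baseline with its own free slope, and that second part is ANCOVA. The random-intercept model ties the slope to the assumption of equal variances, so the split is lost.

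If the spread of 6MWD changes over six weeks of recovery, the standard error of the primary effect is wrong. It is too small if the spread grows (too many false positives) and too large if it shrinks (intervals too wide). The 24-week model also forces equal correlation between every pair of visits.

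**Working it through.** **The plan's own figure.** Inputs from section 3.3: difference 50 m, SDs of change 99 and 71 m, power 80%, alpha 5% (taken as two-sided).
- Pooled variance = (99² + 71²)/2 = 7421, so pooled SD = 86.1 m.
- n per arm = 2 × (1.96 + 0.8416)² × 7421/50² = 46.6. With the noncentral t, 48 per arm gives power 0.80.
- 96/0.8 = 120.

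The sample size reproduces and is not affected by this point.

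**Closed form.** Take complete data, n per arm and no centre effect. Let D0 and D6 be the between-arm differences at baseline and week 6. V0, V6 and cov are the variances and covariance, averaged over arms.
- Random-intercept cLDA: estimate = D6 − ρ·D0, with ρ = 2cov/(V0+V6).
- ANCOVA: estimate = D6 − β·D0, with β = cov/V0. The two slopes agree only if V0 = V6 (or cov = 0).
- Variance reported by the random-intercept model: (2/n) × (V0+V6)/2 × (1 − ρ²).
- True variance of the same estimate: (2/n) × (V6 − 2ρ·cov + ρ²V0). Since cov = ρ(V0+V6)/2, this equals (2/n) × V6 × (1 − ρ²).
- True/reported variance = 2V6/(V0+V6) = 2k²/(1+k²), where k is the week-6/baseline SD ratio.
- Actual type I error = 2[1 − Φ(1.96/√(2k²/(1+k²)))].

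| k (assumed) | true/reported variance | type I error |
|---|---|---|
| 0.8 | 0.78 | 2.7% |
| 0.9 | 0.90 | 3.8% |
| 1.0 | 1.00 | 5.0% |
| 1.1 | 1.10 | 6.1% |
| 1.25 | 1.22 | 7.6% |
| 1.4 | 1.32 | 8.9% |

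**Simulation** (48 per arm, ML fit with z test, centre omitted; ranges are over repeated runs):
- SD 100→120 m, r = 0.7: type I error 7.3–7.9%.
- SD 100→80 m, r = 0.7: 2.7–3.3%.
- SD 100 m at baseline, 159 m (control) and 118 m (intervention) at week 6, r = 0.8, which reproduces the change SDs of 99 and 71: 8.1–9.6% (closed form 8.8%).
- ANCOVA on the same data: 4.4–5.8%.

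**Equivalence, checked directly.** In three complete datasets from the last setting, the random-intercept model estimated 11.3, −4.8 and 11.1 m. ANCOVA gave 24.1, −12.3 and −9.1 m.

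**Do 99 and 71 alone cause the problem?** Take an SD of 160 m at both visits in both arms.
- Control: r = 1 − 99²/(2 × 160²) = 0.809.
- Intervention: r = 1 − 71²/(2 × 160²) = 0.902.

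This meets every figure in section 3.3, and k = 1. The closed-form model SE equals the true SE (16.9 m). Simulated type I error is about 5.6–5.8%, against 5.0–5.3% for ANCOVA; the small excess fits the use of ML with a z test.

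**Robust standard errors.** Applied unconditionally, they bring the simulated changing-variance cases to about 5.5–6.2%. The SAP's trigger would not call for them, because normally distributed data with changing variance pass a qq-plot check.

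**The case against.** A reader might infer that, because the model allows only one SD of change while section 3.3 assumes 99 and 71 m, the primary CI and p-value must be wrong. The documents do not support that. Under 1:1 allocation ("Pragmatic, multi-center, randomized-controlled, 1:1 parallel group trial") with complete data, differences between arms average out, and the 160 m example satisfies all the planning figures with a correctly sized test. Ordinary ANCOVA also has one residual variance for both arms and held close to 5% throughout. The mismatch with section 3.3 is real as a description of the data but is not in itself an error of inference. That example is narrow, though: with equal variance at both visits and r of at least 0.8, a control change SD of 99 m needs a 6MWD SD of at least 99/√0.4 = 156.5 m.

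It is also fair to say that the 8–10% figures rest on an assumed baseline SD of 100 m, and that with complete randomised data the estimate is unbiased, so that the standard error is what fails. Nor is the loss of power large at the planned effect. For SD 100→80 m with r = 0.7 and a 50 m difference, power is about 98% under the specified model and 99% under ANCOVA.

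What the objection leaves standing is that the equivalence sentence is wrong for the model as written, and that nothing in the plan ensures equal variances or protects against unequal ones.

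**Conclusion.** The point holds in a limited form. The model in section 6.2 is equivalent to ANCOVA only if the 6MWD variance is the same at baseline and week 6. If it is not, the primary CI and p-value are mis-sized: too narrow an interval if the spread grows, too wide if it shrinks. For an SD ratio from 0.8 to 1.4, actual type I error is about 3% to 9%. The ratio is an assumption, since the SAP gives no visit SDs, so neither the direction nor the size can be read from the document. The figures assume complete data, equal arms and no centre effect. No calculation was run for the 24-week model or the secondary outcomes; the concern extends to them because they use the same structure. Severity: should-fix.

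**What to change.** In section 6.2, replace the random intercept with an unstructured residual covariance over visits, fitted by REML with small-sample degrees of freedom where the software supports them. Use it for the primary outcome and for all continuous secondary outcomes, including the 24-week model. A matrix common to both arms is enough; separate matrices by arm are optional if the 99/71 assumption is to be carried into the analysis. Limit the ANCOVA sentence to the model with the common unstructured matrix.

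At minimum, make the sandwich standard errors unconditional and remove the equivalence sentence. This is the weaker remedy. It corrects the standard error but leaves the baseline slope as it is, and with dropout that depends on baseline a wrong slope can bias the estimate. In one simulation with SD 100→140 m, r = 0.8, no true effect and about 20% dropout per arm (baseline-dependent in the intervention arm only), the random-intercept model showed a spurious 6.6 m. That size depends on the assumed dropout.

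The cost is one model option and a few covariance parameters. The random intercept uses 2; a common unstructured matrix needs 3 for two visits and 6 for three, doubled if fitted by arm.

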3.2 Randomization and allocation concealment

Permutated block-randomization stratified by study center (block size permuted in the range of 10-14) with allocation concealed by central randomization.

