6.1 Outcome definitions

Primary outcome: The primary outcome of this trial is change in distance walked in meters within six minutes (6MWD) from baseline to 6 weeks (end of intervention program) assessed with the 6-minutes walking test (6MWT).(6, 9)

Secondary outcomes

- (1) Change in 6MWD in meters from baseline to 24 weeks.
- (2) Pulmonary function assessed with a portable pulmonary function device according to the guidelines of the American Thoracic Society.(10, 11) Parameters to be measured include forced

vital capacity (FVC), forced expiratory volume in the first second (FEV1), the ratio of FEV1 and FVC (FEV1/FVC), Peak Expiratory Flow (PEF), and Maximum Voluntary Ventilation (MVV). Percent of predicted value for FEV1, FVC, and FEV1/FVC will be calculated based on Global Lung Initiative (GLI-2012) equations for South-East Asia(12). Percent of predicted PEF and MVV will be calculated based on equations for mainland China provided by Mu and Liu(13).

(3) Perceived dyspnea assessed with the modified Medical Research Council scale (mMRC)(14). This is a patient-reported ordinal scale which distinguishes five grades of dyspnea with 0 indicating no dyspnea and 5 indicating extreme problems with breathlessness making it impossible to leave the house or occurring while dressing or undressing. Given that patients will be included in this trial only if they have baseline mMRC scores of 2-3, an mMRC score of zero is defined as a favorable outcome.

(4) Lower limb muscle strength and endurance measured with the static squat test(15). Participants are asked to perform a squat with their back against the wall starting from a standing position, feet flat on the ground, and approximating a 90° angle at the hip and knees. The time in seconds participants can remain in this squatting positions will be recorded.

(5) Quality of life evaluated with Short Form Health Survey-12 (SF-12) Version 2 (16, 17) reported as two composite scores: Physical Health and Mental Health Composite score, with higher score indicating better health. Scores will be standardized according to US norms(17, 18) for reasons of international comparability and due to lack of general population reference data for mainland China.

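### Center enters the primary cLDA only as a main effect, so the treatment effect on change in 6MWD is only partly center-adjusted and its standard error may be too large

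*SAP*

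**What the plan says.** SAP 3.2 describes the allocation as "Permutated block-randomization stratified by study center". SAP 6.1 defines the endpoint: "The primary outcome of this trial is change in distance walked in meters within six minutes (6MWD) from baseline to 6 weeks".

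For the main analysis, SAP 6.2 states that "a linear mixed effects model with a random intercept for subject will be fitted", regressing 6MWD at the two visits "on study center, time point of assessment and an interaction of time point and intervention group". The Adjustments paragraph of 6.2 adds: "All main analysis of treatment effects will be adjusted for study center (as fixed effect". Neither place names a center-by-time term, and the Missing data paragraph lists the model variables as center, time point and the group-by-time interaction only.

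Of this type of model, 6.2 also says: "In fact, it is equivalent to ANCOVA in the absence of missing outcome data". The 24-week 6MWD analysis and the continuous secondary outcomes follow the same structure with a further visit added.

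**The concern.** The baseline value is an outcome in this model, not a covariate. A covariate entered only as a main effect then explains the level of 6MWD at both visits and says nothing about how much it changes. Center is the factor used to stratify randomization, and centers may well differ in average recovery over six weeks. Such differences stay in the residual.

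Stratified blocks keep the arms nearly balanced within center, so the true sampling variance of the treatment effect largely excludes center differences in change. The model's standard error includes them. At stake are confidence intervals wider than they need be, a test below its nominal 5% level, and some loss of power.

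**Working it through.** **Inputs from the SAP.** Target difference 50 m; SD of change 99 m (control) and 71 m (intervention); power 80%; alpha 5% (taken as two-sided); correlation between visits r ≥ 0.8; 96 analyzed and 120 recruited (all 3.3); 1:1 allocation (3.1).

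**Assumed, because the SAP does not give them.** The number of centers (3 and 5 tried) and the SD between centers of mean change (0, 20, 40 and 60 m tried).

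**1. The plan's own figure.** Mean variance of change = (99² + 71²)/2 = 7421, so SD = 86.1 m. The normal approximation gives 2 × 7421 × (1.96 + 0.84)²/50² = 46.6, or 47 per group. The noncentral t gives 48 per group (power 0.80). Then 96/0.8 = 120. The SAP's numbers are reproduced.

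**2. What the model says about change.** With c_k the center effect, t the time effect, d the treatment effect and g the arm:
- E(y0) = c_k
- E(y1) = c_k + t + d·g
- E(y1 − y0) = t + d·g, with no center term.

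**3. How much center adjustment remains.** With a random intercept and complete data, the difference D = y1 − y0 and the sum S = y0 + y1 are independent. Their variances are proportional to (1 − r) and (1 + r), and each carries the treatment effect d. Weighting by inverse variance:
- weight on D, where center has cancelled: (1 + r)/2
- weight on S, where center remains as 2c_k and is adjusted for: (1 − r)/2.

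At r = 0.8 the weights are 90% and 10%; at r = 0.5 they are 75% and 25%.

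**4. Comparison with an ANCOVA that includes center.** The model implies E(y1 | y0) = (1 − r)c_k + t + d·g + r·y0. An ANCOVA with center estimates the center effect on week 6 freely; here it is forced to (1 − r)c_k. The two agree only if center by time is added.

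**5. Size, with 86.1 m as the within-center SD.** Simulation with N = 96, complete data, stratified blocks of 10, 12 or 14 and r = 0.8, with 3000 runs under the null and 2000 under the alternative. Ranges cover 3 and 5 centers.

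| Between-center SD of change | SE: main effect / with center × time | Power: main effect / with center × time | Type I error: main effect / with center × time |
|---|---|---|---|
| 0 m | 16.6 / 16.6 | 0.84 / 0.84 | 0.047–0.051 / 0.048–0.053 |
| 20 m | 17.0 / 16.65 | 0.84 / 0.85–0.86 | 0.042–0.046 / 0.051 |
| 40 m | 18.2 / 16.6 | 0.78 / 0.83–0.84 | 0.032–0.039 / 0.050–0.053 |
| 60 m | 19.8 / 16.6 | 0.72–0.73 / 0.83–0.84 | 0.023–0.028 / 0.049–0.051 |

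The mean estimate stayed within about 1 m of the true value under both models. At r = 0.5 the power gap is smaller: about 3 to 4 points at 40 m and about 7 at 60 m.

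**6. Size, with 86.1 m as the total SD.** The between-center variance s² is then already inside 7421. For a change-score analysis without center, power is approximately Φ(0.84 × √(7421/(7421 − s²))):
- s = 20: Φ(0.86) = 0.81
- s = 40: Φ(0.95) = 0.83
- s = 60: Φ(1.17) = 0.88.

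Power does not fall below 80%. With center by time, the same approximation is Φ(2.80 × √(7421/(7421 − s²)) − 1.96), which gives about 0.82, 0.89 and 0.97.

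**The case against.** The best defense is that nothing invalid follows. The estimate is essentially unbiased, and the test errs on the conservative side, so no false positive arises from this. That stands for complete data, which is what was simulated. It makes the point one of efficiency.

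A second defense is that the SAP breaks no promise. It says center will be a fixed effect, and it is. The ANCOVA sentence speaks of the type of model in general and does not mention center. This also stands: a reader might infer that the SAP contradicts itself, but the text supports only the narrower statement that the model as written is not equivalent to an ANCOVA that includes center.

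Third, a reader might infer that the model ignores center altogether, or that the planned 80% power is lost. Neither is supported. Center keeps a weight of (1 − r)/2 in the estimate. Section 3.3 takes 99 m and 71 m from an earlier trial and does not say whether they are within-center or total SDs. It bases the 80% on a t-test with no center term. On the total-SD reading the planned power is kept.

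Two possible rescues do not help. Robust standard errors are called for only when residuals look non-normal, and with this mean model they would still contain the center differences in change. The SAP's caution about overfitting concerns auxiliary covariates, whereas center is already in the model.

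**Conclusion.** The concern holds as a matter of precision. The modelled change in 6MWD does not depend on center, and at r = 0.8 only 10% of the weight in the treatment estimate is center-adjusted. If centers differ in mean change, the standard error is too large and the test is conservative.

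The size cannot be fixed from the SAP. At a between-center SD of about 20 m or less it is negligible (1 to 2 power points). With 86 m as the within-center SD and r = 0.8, the model gives up about 5 to 11 points of power at 40 to 60 m; those are large values beside a 50 m target effect. With 86 m as the total SD, the plan keeps its 80% and forgoes a gain. The absence of bias was shown for complete data only. If dropout differed by arm within centers, the within-center balance on which it rests would weaken.

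The correction is still worth making, because it analyzes change by the factor the trial already randomizes by, and no cost was visible when centers do not differ.

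**What to change.** - Add study center by time point to the primary cLDA, keeping the common-baseline constraint for the two arms.
- Add center by each post-baseline visit to the 24-week 6MWD model and to the other continuous secondary models (pulmonary function, squat time, SF-12 composites).
- Do not extend it to the mMRC logistic model. The favorable outcome there is a score of zero, and center-by-visit terms with about 120 participants risk sparse cells.
- Say in 6.2 that the equivalence with a center-adjusted ANCOVA relies on the added term.

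The cost is (centers − 1) degrees of freedom per post-baseline visit. With no center differences, the simulated standard error is 16.6 m with or without the term, and the sample size stays at 96 analyzed and 120 recruited. If some centers turn out very small, the rule for pooling them should be fixed before unblinding.

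### Robust standard errors are made conditional on a visual normality check, which is the wrong trigger: it does not test the constant-variance assumption on which the primary model relies

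*SAP*

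**What the plan says.** Section 6.2 of the SAP analyses 6MWD at baseline and 6 weeks with a mixed model that has a random intercept for subject, with terms for center, time, and time by group. No arm-specific or time-specific variance is named. The secondary continuous outcomes are handled in the same way.

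The paragraph on secondary outcomes then sets the rule for standard errors. The check comes first: "Residuals of all linear models will be checked for normal distribution using qq-plots". The consequence of failing it follows: "if this assumption is violated robust standard errors (Huber-White sandwich estimator) will be calculated". Because the rule covers all linear models, it governs the primary analysis too. No numeric criterion is given for a violation, and the SAP does not say who reads the plot or whether that person is blinded.

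Section 3.3 plans the trial on unequal spread: "A standard deviation of change in 6MWD over six weeks of 99 meters in controls and 71 in the intervention group". It defends the inequality as plausible: "The assumption of a greater standard deviation in controls makes sense in so far as a greater variety of outcomes can be expected".

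**The concern.** The remedy is tied to the wrong assumption. A Huber-White estimator gives valid standard errors when the variance or correlation structure is misspecified. It is not chiefly a cure for non-normal residuals, which matter little for a difference in means at this sample size.

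The assumption more likely to fail is constant variance. A random-intercept model on two visits imposes the same variance at both visits and in both arms, and one within-patient correlation. The planning SDs imply a variance ratio between arms of 99²/71² = 9801/5041 = 1.94, so the SAP itself expects a departure. Residuals can look acceptably normal while that structure is wrong, and the model-based SE would then stand.

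At stake are the confidence interval and p-value of the primary comparison. In borderline results, the reading of a plot without a stated threshold would decide which of two standard errors is reported.

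**Working it through.** **1. The SAP's own figure.** Inputs from section 3.3: "a larger and thus more conservative MID of 50 meters is supposed here", SDs of 99 and 71, power 80%, alpha 5% (two-sided assumed). Per arm, (1.960 + 0.842)² × (9801 + 5041) / 50² = 46.6, so 47 by the normal approximation. With the t distribution, power is 0.795 at 47 and 0.8035 at 48 per arm. The stated 48 per group and 96 in total reproduce, and 96 / 0.8 = 120. The sample size already uses the unequal SDs and is not affected.

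**2. Unequal arm variances alone (simple change scores).** Compare the pooled-variance SE with the true SE.
- 48/48: both variances are (9801 + 5041)/48 = 309.2. The SE ratio is 1.000, so there is no error.
- 44 control / 52 intervention: ratio 0.973, type I error 5.6%.
- 40/56: pooled variance (39 × 9801 + 55 × 5041)/94 = 7016; times (1/40 + 1/56) = 300.7. True: 9801/40 + 5041/56 = 335.0. Ratio √(300.7/335.0) = 0.947; type I error 2 × [1 − Φ(1.96 × 0.947)] = 6.3%.
- 56/40: 335.4 against 301.0, ratio 1.055, type I error 3.9% (conservative).

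**3. Variance change over time alone.** Assume SD 100 m at baseline and 140 m at week 6 in both arms, correlation 0.8, so the covariance is 0.8 × 100 × 140 = 11,200. The model averages the two variances: v = (10,000 + 19,600)/2 = 14,800. Its baseline slope is b = 11,200/14,800 = 0.757.
- Variance the model claims per patient: v(1 − b²) = 6,324.
- True variance: 19,600 − 2b × 11,200 + b² × 10,000 = 8,375.
- SE ratio √(6,324/8,375) = 0.869; type I error 2 × [1 − Φ(1.96 × 0.869)] = 8.9%. Simulation gave 8.2% at 48/48 and 8.4% at 40/56.

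So much of the possible inflation needs no difference between arms. The direction matters: with 140 m falling to 100 m, the true variance is 10,000 − 2b × 11,200 + b² × 19,600 = 4,273, below the claimed 6,324, and the test is conservative.

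**4. Both together.** Simulation of the section 6.2 primary model under no effect: normal data, change SDs of 99 and 71, complete data, 2,500 runs per setting (error about 0.4 to 0.6 points). Assumed, not in the SAP: three centers, baseline SD 90 or 120 m, and the correlation of baseline with change. For the SAP's rule, a Shapiro-Wilk p below 0.05 stands in for the visual reading. Entries are type I error in percent, for baseline SD 90 and then 120.

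| Control/intervention completers | SD from baseline to week 6 | Model-based SE | SAP's rule | Robust SE always |
|---|---|---|---|---|
| 48/48 | unchanged | 5.2, 5.6 | 5.2, 5.6 | 5.6, 5.8 |
| 48/48 | some growth | 6.7, 6.0 | 6.6, 6.0 | 5.7, 5.7 |
| 48/48 | more growth | 8.9, 7.2 | 8.3, 6.9 | 5.4, 4.9 |
| 40/56 | unchanged | 6.5, 6.2 | 6.4, 6.1 | 6.0, 5.5 |
| 40/56 | some growth | 8.3, 7.0 | 8.1, 7.0 | 5.7, 5.8 |
| 40/56 | more growth | 11.8, 9.2 | 10.8, 8.8 | 6.2, 6.0 |
| 56/40 | unchanged | 4.5, 4.3 | 4.6, 4.5 | 5.7, 5.6 |
| 56/40 | some growth | 6.3, 4.4 | 6.2, 4.4 | 5.9, 5.2 |
| 56/40 | more growth | 7.3, 6.5 | 7.0, 6.4 | 5.3, 5.6 |

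Week-6 SDs, control/intervention, follow from SD₁² = SD₀² + SD_change² + 2ρ × SD₀ × SD_change. From 90 they are 112/97 (ρ = −0.3) and 134/115 (ρ = 0); from 120 they are 131/120 and 156/139. In the unchanged rows the arms differ only in within-patient correlation.

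Over all settings run (60/60 and 36/60 included), the stand-in trigger fired in 5 to 19% of runs, so the model-based SE stayed in use in 81 to 95%. The two SEs gave different verdicts at 0.05 in 0.4 to 5.6% of runs.

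**The case against.** A reader might infer that the 99 and 71 m in section 3.3 are enough to corrupt the primary p-value, with a type I error near 11%. The document does not support that. Allocation is 1:1 ("Pragmatic, multi-center, randomized-controlled, 1:1 parallel group trial"), and at equal arms the inequality costs almost nothing (step 2 and the unchanged rows). A 40/56 split out of 60/60 means 33% dropout in controls against 7% in the intervention group, whereas section 3.3 assumes 20% overall and no differential. The opposite split can make the model-based test conservative. The highest figures need variance growth over time, and the SAP gives neither baseline nor 6-week SDs.

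A reader might also call this a post-hoc choice of analysis. The diagnostic, the trigger and the remedy are all written in advance; only the reading of a violation is open.

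Finally, a residual check with a robust fallback is a common convention, and the fallback does no harm when used. Nor was the qq-plot itself simulated: a formal normality test stood in for a human reader, who may be stricter or more lenient.

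These points limit the size. They do not rescue the trigger: variance growth is also a fault of variance structure, a normality check is not designed to find it, and robust SEs correct the standard error in either case.

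**Conclusion.** The point holds as a defect in how the standard error is chosen, with a size that cannot be fixed from the SAP. Three levels should be kept apart:
- Equal arms and similar average spread at both visits: about 5 to 6%, so essentially no harm.
- Fewer control than intervention completers (40/56): about 6 to 7% from unequal arm variances alone.
- Spread also growing from baseline to week 6: about 8 to 11% when the growth is marked. The highest single setting was 11.8% model-based and 10.8% under the SAP's rule. Most of this comes from holding variance constant over time.

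Robust SEs used in every run kept type I error between 4.9 and 6.2%. All of this rests on the assumed SDs, correlations and completion split, on complete data, and on the stand-in for the visual check.

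**What to change.** In section 6.2, remove the qq-plot as the condition for robust SEs. State that all linear mixed models, the primary one included, use subject-clustered robust standard errors unconditionally. The alternative is to model arm- and time-specific residual variances. Keep qq-plots as a descriptive check.

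The cost is one sentence and one model option, with no change to the sample size. If the variances are in fact equal, the standard errors are slightly less stable and coverage falls very slightly short with about 100 clusters. The modelled-variance alternative adds a few parameters; in return it also weights the visits appropriately when week-6 values are missing, whereas a sandwich estimator corrects only the standard error.
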